12.1 Definition of an Adverse Event

An AE is any untoward medical occurrence in a subject or clinical investigation subject administered a pharmaceutical product that does not necessarily have a causal relationship with this study medication. An AE can therefore be any unfavorable and unintended sign (including an abnormal laboratory finding, for example), symptom, or disease temporally associated with the use of a study medication, whether or not considered related to the study medication.

12.2 Adverse Events of Special Interest

AESIs will be collected for the following:

All bone fractures

All AESIs (including event management and evaluation) will be recorded and reported similar to SAEs as described in Section 12.8. MT-2990 does not have any hormonal effects and is not anticipated to have any impact on bone mineral density. However, this population has been exposed to other hormonal treatments prior to study entry, increasing the risk of osteoporosis and possible fractures.

12.3 Definition of a Serious Adverse Event

An SAE is defined as any untoward medical occurrence that at any dose:

- · Results in death
- Is life-threatening
- Requires hospitalization or prolongation of existing hospitalization
- Results in persistent or significant disability or incapacity
- Is a congenital anomaly or birth defect
- Is an important medical event

Medical and scientific judgement should be exercised in deciding whether an AE is serious and whether expedited reporting is appropriate in other situations, such as important medical events that may not be immediately life-threatening or result in death or hospitalization but may jeopardize the subject or may require medical or surgical intervention to prevent 1 of the other outcomes listed in the above definition. These should also be considered serious.

Examples of such events are invasive or malignant cancers, intensive treatment in an emergency room or at home for allergic bronchospasm, blood dyscrasias or convulsions that do not result in hospitalization, or development of drug dependency or drug abuse. These should also usually be considered serious.

The term 'life-threatening' refers to an event/reaction in which the subject was at risk of death at the time of the event/reaction; it does not refer to an event/reaction, which hypothetically might have caused death if it were more severe.

Admission to a hospital as a new inpatient is deemed as meeting this criterion, even when the length of hospital stay was less than 24 hours. Transfer to other departments of the same hospital due to a newly emerged event during the hospitalization (eg, transfer from the psychiatry ward to the internal medicine ward, from the internal medicine ward to the coronary intensive care unit, or from the neurology ward to the tuberculosis [TB] ward) is also counted as hospitalization.

SAEs will be recorded and reported as described in Section 12.8.

12.4 Severity of Adverse Events

The severity of AEs will be classified according to the following criteria: Mild: The event is transient and easily tolerated by the subject.

Moderate: condition.

The event causes discomfort and interferes with the subject's general

Severe:

The event causes considerable interference with the subject's general condition and may be incapacitating.

To ensure no confusion or misunderstanding of the difference between the terms 'serious' and 'severe', which are not synonymous, the following note of clarification is provided:

The term 'severe' is often used to describe the severity of a specific event (as in mild, moderate, or severe myocardial infarction); the event itself, however, may be of relatively minor medical significance (such as severe headache). This is not the same as 'serious', which is based on subject/event outcome or action criteria usually associated with events that pose a threat to a subject's life or functioning. Seriousness (not severity) serves as a guide for defining regulatory reporting obligations.

12.5 Relationship of Adverse Events to Investigational Medicinal Product

The causal relationship of the AE to study medication will be determined as either

'reasonable possibility' or 'no reasonable possibility' defined as:

Reasonable Possibility – The relationship of the clinical event to the study medication makes a causal relationship possible, and other drugs, therapeutic interventions, or underlying conditions do not provide a sufficient explanation for the observed event.

No Reasonable Possibility – The relationship of the clinical event to the study medication makes a causal relationship unlikely, or other drugs, therapeutic interventions or underlying conditions provide a sufficient explanation for the observed event.

12.6 Clinical Laboratory Abnormalities and Other Abnormal Assessments

Laboratory abnormalities, which are CS, will be recorded as AEs or SAEs. The Investigator will exercise medical judgement in deciding whether abnormal laboratory values are CS.

If an abnormal laboratory value or assessment is clearly related to a medically-defined diagnosis or syndrome, the diagnosis or syndrome will be recorded on the AE form, not the individual laboratory values.

All CS abnormal laboratory results or assessments will be followed until they resolve (return to normal or Screening values) or stabilize, or until they are judged by the Investigator to be no longer CS.

12.7 Recording and Reporting of Adverse Events

All AEs, regardless of the relationship to study medication, occurring from Day 1, will be obtained from a subject until the end of the Double-blind Treatment Period (Visit 9) or the withdrawal of the subject from the study will be recorded.

NOTE: Elective hospitalization or procedure/surgery planned before subject enrollment for a preexisting medical condition does not constitute an AE unless the underlying disease or condition worsens after Day 1.

All AEs will be recorded on an AE form in the eCRF. Reports should contain a description of the event, date and time of onset, date and time of resolution, severity, treatment required, relationship to study medication, action taken with the study medication, outcome and whether the event is classified as serious.

The Investigator will evaluate the severity of the AEs (as defined in Section 12.4) and will assess the causality between the AEs and the study medication (as defined in Section 12.5).

Pre-existing illnesses, which started prior to entry and are still ongoing at the start of the study, will not be considered AEs unless they worsen during the Double-blind Treatment period. Pre-existing conditions will be recorded as medical history.

If the Investigator becomes aware of any new safety information, or any safety information, which appears to be either study or study medication related after the Double-blind Treatment period, then they must notify the Sponsor immediately. This information does not require reporting of an AE on the eCRF, but should still be communicated to the Sponsor.

12.8 Recording and Reporting of Serious Adverse Events or Adverse Events of Special Interest

All SAEs occurring from the time written ICF is obtained from a subject until the end of the Double-blind Treatment Period or the withdrawal of the subject from the study must be reported to the Sponsor or the designee using the SAE/AESI Form in Clinical Study within 24 hours of the Investigator becoming aware of the SAE. All SAEs and AESI must also be entered in the AE section of the eCRF within 24 hours.

SAE report should be completed as thoroughly as possible, including an assessment of causality. All such reports will identify subjects by unique code numbers assigned to the study participants, rather than by the subjects' names, personal identification numbers, or addresses.

The reporting contact for SAEs/AESI is as follows:

In case of any email problems, the SAE/AESI form will be sent to the Sponsor or the designee Safety via fax to:

The Sponsor will comply with the applicable regulatory requirements related to the reporting of Suspected Unexpected Serious Adverse Reactions (SUSARs) to the regulatory authorities and central IRB(s). The Investigator will be responsible for informing the local IRB(s) of relevant safety information, including SUSARs, as per local laws and requirements.

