7 STUDY DESIGN

7.1 Overall Study Design

7.1.1 Study Methodology

This is a Phase 2, randomized, double-blind, placebo-controlled study, stratified by moderate or severe pain to evaluate safety and efficacy of MT-2990 in women with endometriosis-associated moderate to severe pain. Approximately 76 subjects will be randomized into the study, with approximately 38 subjects in each treatment arm. The approximate duration of the study per subject is 52 weeks, inclusive of the Screening period, Double-blind Treatment period, and the Extended Follow-up period.

Following the Screening period, eligible subjects who have met all the eligibility criteria and have moderate or severe nonmenstrual pelvic pain, and dysmenorrhea will be randomized into the study. Approximately 38 subjects per arm will be enrolled. Subjects will be randomly allocated to 1 of 2 treatment groups (placebo or MT-2990 in a ratio of 1:1.

All efficacy and safety measures will be collected during the 16-week Double-blind Treatment period.

End-of-treatment (EOT) will occur at Week 12 (Visit 7) and primary and secondary efficacy endpoints will be assessed at the Week 16 (Visit 9) visit. Subjects who discontinue from the study will complete the procedures for Visit 9 within 10 days of discontinuation (or as soon as possible after the site becomes aware of the discontinuation).

During the Extended Follow-up period, visits will be conducted via a telephone call at Week 27 (Visit 10) and at Week 38 (Visit 11).

The Sponsor will be unblinded after Week 16 (Visit 9), while the Sites and subjects will remain blinded until the end of the Extended Follow-up period at Week 38 (Visit 11). During the study, database will be locked twice: at Week 16 (Visit 9) to assess safety and efficacy, and at Week 38 (Visit 11) to assess other outcomes during the Extended Follow-up period.

There will be 3 interim assessments for safety. The first interim assessment for safety will be performed when 20 subjects are randomized and have completed the Week 2 visit. The second interim assessment for safety will be performed when 50% of the subjects are randomized and have completed the Week 4 visit. The third interim assessment for safety will be performed when 50% of the subjects are randomized and have completed the Week 16 visit.

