In the event that a subject elects not to return to the clinical site for the ET Visit, the Investigator must make every effort to contact the subject to review all AEs. In the event that a subject drops out of the study at any time, the reason for discontinuation must be fully documented in the source documents and the eCRF. The Investigator site personnel will document the AEs and any other assessments in the source documents and will make every effort to complete all required ET assessments.

Subjects who are withdrawn from the study following randomization may not re-enter the study.

The study may be terminated by the sponsor at any time upon becoming aware of data that could compromise the safety and/or well-being of subject or for any other reason it deems appropriate.

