10.18.2 Vital signs

Sitting blood pressure (systolic and diastolic) will be measured at all study visits, including Screening where vital signs are to be assessed. Sitting blood pressure will be measured using an automatic blood pressure recording device with an appropriate cuff size, after the subject has rested for at least 5 minutes in a sitting position. The same arm will be used for all measurements where possible. The Investigator will perform an overall evaluation of vital sign findings outside of the normal range for safety purposes; such results will be reported as either 'abnormal clinically significant (CS)', or 'abnormal not CS (NCS)'. Pulse rate and tympanic body temperature will also be measured. Abnormalities of clinical significance will be reported as AEs. Repeat measurements will be performed, if needed. In addition, at Visit 2, 5, 6 and 7, vital signs will also be measured at 15±5 minutes, 30±5 minutes and 60±10 minutes post study drug infusion.

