12 ADVERSE EVENT MANAGEMENT

All AEs and SAEs will be recorded in the source documents. All SAEs that occur from the time written ICF is obtained until the end of the Double-blind Treatment Period (Visit 9), and all AEs that occur from Day 1 until the end of the Double-blind Treatment Period (Visit 9) will be recorded in the eCRF. Even if the AE is assessed by the Investigator as not related to study medication, its occurrence must be recorded in the source documents and eCRF. AEs will be classified as 'treatment-emergent' if they arise following the administration of study medication or if a predose illness increases in severity following dosing.

At each study visit, after the subject has had an opportunity to spontaneously mention any problems, the Investigator should inquire about the occurrence of AEs. The questioning should be open-ended and nonleading.

Post each study drug infusion, subject should be observed for approximately 60 ± 10 minutes. During this period, vital signs must be obtained at 15 ± 5 minutes, 30 ± 5 minutes and 60 ± 10 minutes. A patient instructions sheet will be provided to all subjects with instructions to observe and report all possible adverse events such as infusion related or infections in particular.

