### (2) Treatment Compliance

The subjects are supposed to take a dose every four weeks and totally 4 doses per protocol. Treatment compliance (%) =number of doses/ROUNDUP(treatment duration/28).

[figure not shown]

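### Sections 12, 12.7 and 12.8 of the protocol end adverse event recording at different points for women who leave, so new events after an early withdrawal have 0 to about 10 days of recording after the last infusion, against a nominal 28 for completers

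*Protocol*

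**What the plan says.** **End of recording**
- Section 12 has one end point for every subject: "all AEs that occur from Day 1 until the end of the Double-blind Treatment Period (Visit 9) will be recorded in the eCRF". The same sentence ends SAE recording at Visit 9. It does not mention withdrawal.
- Section 12.7 collects AEs from Day 1 "until the end of the Double-blind Treatment Period (Visit 9) or the withdrawal of the subject from the study".
- Section 12.8 covers SAEs from consent "until the end of the Double-blind Treatment Period or the withdrawal of the subject from the study must be reported to the Sponsor". Section 12.2 sends fractures, the only AESI, down the SAE route.

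**Women who leave**
- Section 7.1.1: "Subjects who discontinue from the study will complete the procedures for Visit 9 within 10 days of discontinuation", or as soon as the site can arrange it once it knows. Section 9.1.5 labels Visit 9 as the ET visit.
- If she does not return, Section 8.5 says "the Investigator must make every effort to contact the subject to review all AEs".
- Section 8.5 makes hypersensitivity and moderate to severe infusion-related reactions grounds for withdrawal, along with certain blood count and liver findings.
- Section 12.10 follows existing AEs and SAEs until they resolve or stabilize.
- Section 12.7 also asks for immediate notice to the sponsor of study-related or drug-related safety information that emerges after the double-blind period, but states that no eCRF entry is needed.

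**Dosing and analysis**
- SAP 7.1.1.2 says that subjects are "supposed to take a dose every four weeks and totally 4 doses per protocol". Protocol Section 10.18.2 places the post-infusion checks "at Visit 2, 5, 6 and 7, vital signs will also be measured", and Visit 7 is Week 12.
- SAP 8.3.1 counts subjects with treatment-emergent AEs (TEAEs), and SAP 6.1 takes all subjects in the group as the denominator. SAP 7.1.3.1 defines a TEAE without an end date.

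**The concern.** The end-of-recording rule decides which events reach the database, and for a woman who leaves the protocol states it in two ways. A site following Section 12 would record a new event found at the ET visit. A site following 12.7 could leave the same event out because it began after withdrawal, even though Section 8.5 asks for AEs to be reviewed at that contact. About 38 sites are planned, so both readings are likely to be used.

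The women most exposed are those withdrawn soon after an infusion, for example for a hypersensitivity or infusion-related reaction. Their post-dose recording can be much shorter than a completer's. The SAP counts subjects with events, makes no stated adjustment for observation time, and sets no TEAE end date that would standardise the window. The tables therefore depend on what sites decide to enter. The DMC, whose stated focus includes hypersensitivity and immune reactions, works from the same recorded events.

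**Working it through.** **Inputs**
- Dosing every four weeks, four doses (SAP 7.1.1.2), infusions at Visits 2, 5, 6 and 7 (Protocol 10.18.2).
- Nominal days for Week 12 and Week 16: Day 85 and Day 113 (SAP 7.3).
- ET visit within 10 days of discontinuation (Protocol 7.1.1).
- 76 randomized, 25% drop-out allowance (Protocol 14.1).

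**1. Reproduce the nominal days.** Nominal day = 7 × week + 1.
- Week 12: 7 × 12 + 1 = 85. Week 16: 7 × 16 + 1 = 113. Both agree with the SAP.
- Doses at Weeks 0, 4, 8 and 12 fall on Days 1, 29, 57 and 85.

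**2. Completers.** Last dose to Visit 9: 113 − 85 = 28 days. The plan does not state this as a follow-up target; it is a result of the visit schedule, and actual dates will vary.

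**3. A woman withdrawn on an infusion day.** Days after that dose in which a new event falls inside the recording period:

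| Reading | Days |
|---|---|
| 12.7 and 12.8 literally, withdrawal dated that day | 0 |
| Section 12, with the ET visit as her Visit 9, on time | 0 to about 10 |
| Section 12, with Visit 9 as scheduled Week 16 | 112, 84, 56 or 28 after dose 1, 2, 3 or 4 |

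The third row is 113 minus the dose day. It fits poorly with Sections 7.1.1 and 9.1.5, which bring Visit 9 forward for women who discontinue. The range that the documents support is the first two rows: 0 to about 10 days, longer if the ET visit is late.

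**4. Shortfall against completers.** 28 − 10 = 18 days to 28 − 0 = 28 days.

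**5. Leaving some time after a dose.** If she leaves k days after her last dose, recording runs k days under 12.7 and 12.8, or up to k + 10 under Section 12. The shortfall is 28 − k or 18 − k. It disappears at k = 28 under the first reading and at k = 18 under the second, given an ET visit on day 10 after leaving. The problem is therefore confined to women who leave fairly soon after an infusion.

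**6. How many.** 0.25 × 76 = 19 women is the all-cause drop-out allowance. The documents give no figure for safety withdrawals or for withdrawals close to a dose, so 19 is only an upper limit under the planning assumption.

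**7. Do other sections close the gap?** Section 12.10 covers events already open, not new ones. The AE review at or in place of the ET visit finds new events, but 12.7 leaves it unclear whether those starting after withdrawal are recorded. The late-information clause in 12.7 reaches the sponsor, not the eCRF.

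**The case against.** The strongest reply is that the protocol treats withdrawal as a process that ends with the ET visit. Read that way, withdrawal in 12.7 and 12.8 means completed exit, the three sections agree, and the site reviews all AEs at that visit or by contact. The ET column of Table 2 may also call for AE collection; the table is not in the text available, so this could not be checked. Serious late events have other routes: the duty to notify the sponsor, and SUSAR reporting to the DMC in real time.

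Part of this stands. Zero days is the lower limit and not the planned course, and late drug-related information is not without a route. But the documents never define the withdrawal date, so the reconciling reading is not secured. Even under it, a woman who leaves on an infusion day has about 10 days if the visit is on time, not 28. Notification outside the eCRF does not put an event into the SAP tables.

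A reader might infer several stronger things that the documents do not support:
- *That the reactions themselves go unrecorded.* The reaction that prompts withdrawal occurs before it, is recorded, is followed under 12.10, and counts in the rows for any TEAE and for TEAEs leading to discontinuation.
- *That all women withdrawn for safety have the shortest follow-up.* Blood count and liver withdrawals rest on laboratory results and need not fall near a dose.
- *That 19 women are affected.* That figure is the all-cause allowance used to size the trial.
- *That the comparison is biased towards no difference.* This needs more early safety withdrawals on MT-2990 than on placebo, which is not known in advance.

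**Conclusion.** The inconsistency is real and stands in the current text. For a woman withdrawn on an infusion day, new AEs and SAEs fall inside the recording period for 0 to about 10 days, against a nominal 28 for completers: a shortfall of 18 to 28 days, which shrinks day for day the longer after a dose she leaves.

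This rests on nominal visit days, on an ET visit held on time, and on Visit 9 meaning the ET visit for women who discontinue. What is at risk is new, later events only. The number of women is unknown, with 19 of 76 as a ceiling under the planned drop-out rate.

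If withdrawals of this kind are equally common in both arms, the counts are incomplete but the shorter window does not by itself favour either arm. If they are more common on MT-2990, its later events are under-recorded relative to placebo; if more common on placebo, the reverse. The point deserves correction because it concerns completeness of safety data and is cheap to settle, not because a bias has been shown.

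**What to change.** Give Sections 12, 12.7 and 12.8 one end date for women who leave:
- Remove withdrawal from the study as an alternative end of recording in 12.7 and 12.8.
- Record new AEs, SAEs and AESIs in the eCRF through the later of the ET visit and 28 days after the last dose. Twenty-eight days is the nominal interval that completers already get.
- Where the ET visit comes sooner than 28 days, complete the period by telephone, unless the woman withdraws consent for contact.
- Make the ET column of Table 2 agree.

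Reconciling the sections is the minimum. The 28-day floor goes further: it makes the post-dose window of early leavers comparable with that of completers. Neither change touches dosing or the withdrawal criteria.

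The cost is amendment wording and at most one call per early leaver. Some women will decline, so the shortfall will be reduced but not removed.

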12.9 Pregnancy

If a female subject who has been exposed to the study medication becomes pregnant, the course and outcome of the pregnancy should be monitored and documented.

Pregnancy occurring in a female subject who has been exposed to the study medication, although not classified as an SAE, must be reported using the same timelines and contact details as an SAE (Section 12.8) via a paper *Pregnancy Notification Form in Clinical Study* form. If the outcome or course of the pregnancy involves an SAE (eg, a congenital anomaly or spontaneous abortion), then the *SAE/AESI Form in Clinical Study* needs to be completed.

Subjects who become pregnant while on study should be withdrawn from treatment, as described in Section 8.5.

12.10 Follow-up of Adverse Events

The Investigator should follow-up with subjects with AEs/SAEs, until the event has resolved or stabilized and any abnormal laboratory values have returned to Baseline; or until there is a satisfactory explanation for the changes observed. In the case of death, if possible, a pathologist's full report should be supplied.

